Due to the design of the study, there will be no formal hypothesis testing. Descriptive summary statistics such as number, percentage for categorical endpoints and mean, standard deviation, median for continuous endpoints will be summarized by the following four subgroups of subjects based on the status at baseline of Study A3921139: 1) in remission defined by a total Mayo score ≤ 2 with no individual subscore > 1 , and rectal bleeding subscore of 0, 2) treatment failure defined by an increase in Mayo score of at least 3 points from baseline value of the maintenance study (A3921096), accompanied by an increase in rectal bleeding subscore by at least 1 point, and an increase of endoscopic subscore of at least 1 point (yielding an absolute endoscopic subscore of ≥ 2), 3) all other subjects from maintenance study A3921096 neither in remission nor fulfilling the definition of treatment failure, and 4) non-responders from induction studies A3921094 or A3921095.

Safety Analysis

The safety data will be summarized in accordance with Pfizer Data Standards based on the safety analysis set defined as all subjects who receive at least 1 dose of study medication.

SCHEDULE OF ACTIVITIES

The Schedule of Activities table provides an overview of the protocol visits and procedures. Refer to Study Procedures ([Section 6](#)) and Assessments ([Section 7](#)) for detailed information on each procedure and assessment required for compliance with the protocol.

All study visits during the first year will have a window of ± 5 days. The 4-week follow-up evaluation visit and all study visits in subsequent years will have a window of ± 7 days.

This study will continue until approximately July 2020. Individual subject duration of participation will vary depending on when the subject was enrolled into the study and the end date of approximately July 2020. Therefore, the duration of participation for an individual subject may range from approximately 4 years to more than 7 years. Annual schedule of activities are identical from year 4 and beyond. For illustration purposes, the [Schedule of Activities](#) contains study procedures up to Month 72 (year 6). If the study continues beyond year 6 for an individual subject, the investigator should continue to follow the same visit schedule and study procedures outlined during the study visits of year 4.

Schedule of activities for first year:

| Study Procedure | Baseline | Open Label Treatment Period | | | | | |

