6.3. Subject Withdrawal

Should a subject withdraw from active treatment, the subject should complete the procedures listed at the Month 12/ET Visit. After completing the procedures for the early withdrawal visit, the subject should return for a safety evaluation to occur approximately 4 weeks after discontinuing study medication as per the follow-up visit.

Subjects will be withdrawn from the study if any of the following occurs during the study treatment period:

- If a subject who enrolled from the induction studies A3921094 or A3921095 (ie, non-responders) fails to demonstrate clinical response at Month 2. Clinical response is defined by a decrease from the induction study baseline (A3921094 or A3921095) Mayo score of at least 3 points and at least 30%, with an accompanying decrease in the rectal bleeding subscore of at least 1 point or an absolute rectal bleeding subscore of 0 or 1. The endoscopic subscore based on central reading will be used to assess clinical response.
- If rescue therapy is initiated for UC with the exception of oral 5-ASA or sulfasalazine. Rescue therapy includes re-initiation of oral corticosteroid therapy above 10 mg/day of prednisone or equivalent after a subject has achieved steroid-free status during either Study A3921096 or A3921139.
- If a subject undergoes surgery for UC.
- If a subject remains on oral corticosteroids exceeding 15 mg/day of prednisone or equivalent after Month 3.

A subject may be withdrawn from the study for any of the safety concerns as listed in [Appendix 3](#).

Subjects who develop a serious infection during the study, defined as any infection (viral, bacterial, and fungal) requiring hospitalization or parenteral antimicrobials or being classified as a serious adverse event should be withdrawn from the study (see [Section 7.3.10](#)).

All abnormal laboratory events of clinical significance should be followed until the laboratory values have returned to normal or baseline levels (see [Appendix 3](#)). Subjects who meet the discontinuation criteria described in [Appendix 3](#) will be withdrawn from the study.

If a subject has any clinically significant, study-related abnormalities at the conclusion of the study, the Pfizer medical monitor (or designated representative) should be notified and every effort should be made to arrange follow-up evaluations at appropriate intervals to document the course of the abnormalities.

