7. HANDLING OF MISSING VALUES

7.1. Efficacy Endpoints

For binary efficacy endpoints (Remission, Clinical remission, Mucosal healing, PMS remission, Clinical response) derived from Mayo subscores (site-read endoscopic subscore was used), data will be summarized based on the observed-case data and non-responder imputation and last observation carried forward imputation (NRI-LOCF). The NRI-LOCF approach is described as the following:

- For subjects who discontinued from the study, other than those who moved to Study A3921288 or to the Japan post-marketing surveillance study, or due to regulatory approval in Japan, NRI will be used for missing data up to the visit (using the lower bound of visit window as defined in [Appendix 1](#)) they would have reached if they had stayed at the study. The missing data before time of discontinuation will be imputed as non-responders.
- For ongoing subjects (for interim analyses only), they will be included in the summary tables only up to visits with non-missing data in the dataset for the interim report. For subjects with intermittent missing data, they will be treated as non-responders. Otherwise no imputation for missing data will be applied since it's hard to separate the true missing data from being late for the scheduled visit.
- For completed subjects, they will be included in the summary tables only up to the completion visit. Missing data before the completion will be imputed using the NRI approach.
- For subjects who discontinued from the study and moved to Study A3921288 or to the Japan post-marketing surveillance study, or due to regulatory approval in Japan, LOCF will be used up to the visit (using the lower bound of visit window as defined in [Appendix 1](#)) they would have reached if they had stayed in the study. The missing data before time of discontinuation will be imputed as non-responders. This approach will likely overestimate the proportions of subjects who achieve the binary endpoints since it is assumed that the response status remains after subjects moved to Study A3921288 or the Japan post-marketing surveillance study.

For continuous endpoints total Mayo score and Partial Mayo score, data will be summarized based on the observed-case data and LOCF. The LOCF approach is described as the following:

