7.2. PRO Endpoints

For the PRO endpoints based on IBDQ, CCI [REDACTED] rules suggested by the developers of the questionnaires will be followed in calculating the endpoints with any missing items. If these rules are not sufficient to impute the missing values, then the missing values will be handled as following:

- For IBDQ binary endpoints IBDQ remission and deterioration (worsening) in IBDQ bowel symptom domain, they will be handled in the same way as binary efficacy endpoints as specified in section 7.1 for missing data and data after the dose escalation.
- For IBDQ CCI [REDACTED] continuous endpoints, they will be handled in the same way as continuous efficacy endpoints as specified in section 7.1 for missing data and data after the dose escalation.

CCI [REDACTED]

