8.2.5. Analyses of Patient reported Outcome (PRO) Endpoints

Descriptive summary statistics will be reported at scheduled visits in FAS, and four subpopulations; Maintenance Remission, Maintenance Failure, Other Maintenance Completers, and Induction Non-responders using the same methods as for the efficacy endpoints for IBDQ. ^{CCI} [REDACTED].

CCI [REDACTED]

CCI [REDACTED]

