9. APPENDICES

Appendix 1. Definition of Analysis Visit Windows

Analysis visit windows will be used for efficacy variables, and for any safety displays that display by visit.

Visit Label	Target Day	Analysis Visit window
Baseline	Day 1	Up to Day 1
Month 1	Day 30	Days 2-45
Month 2	Day 60	Days 46-90
Month 4	Day 120	Days 91-150
Month 6	Day 180	Days 151-225
Month 9	Day 270	Days 226-315
Month 12	Day 360	Days 316-405
Month 15	Day 450	Days 406-495
Month 18	Day 540	Days 496-585
Month 21	Day 630	Days 586-675
Month 24	Day 720	Days 676-765
Month 27	Day 810	Days 766-855
Month 30	Day 900	Days 856-945
Month 33	Day 990	Days 946-1035
Month 36	Day 1080	Days 1036-1125
Month 39	Day 1170	Days 1126-1215
Month 42	Day 1260	Days 1216-1305
Month 45	Day 1350	Days 1306-1395
Month 48	Day 1440	Days 1396-1485
Month 51	Day 1530	Days 1486-1575
Month 54	Day 1620	Days 1576-1665
Month 57	Day 1710	Days 1666-1755
Month 60	Day 1800	Days 1756-1845
Month 63	Day 1890	Days 1846-1935
Month 66	Day 1980	Days 1936-2025
Month 69	Day 2070	Days 2026-2115
Month 72	Day 2160	Day 2116-2205
Month 75	Day 2250	Days 2206-2295
Month 78	Day 2340	Days 2296-2385
Month 81	Day 2430	Days 2386-2475
Month \geq 84	Day 2520	Days \geq 2476

If more than one observation from the same subject falls into the same window, the value closest to the target day will be used as the observation for that analysis visit. All observations will, however, be included in the listings.

For efficacy endpoints derived based on total Mayo score we will use the same windows from the above table although total Mayo score was not assessed at each visit.

Some PRO data or laboratory data were not scheduled to be assessed at each visit. In this case, the unscheduled 'windowed' visit will be moved to the next scheduled windowed visit for analysis and reporting.

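### SAP Appendix 1 moves early-termination IBDQ scores forward to a visit the subject never attended, so IBDQ remission can escape non-responder imputation at that visit

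*SAP*

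**What the plan says.** **Visit assignment.** SAP Appendix 1 defines contiguous analysis windows. For PRO and laboratory data not scheduled at every visit, a value in an unscheduled window "visit will be moved to the next scheduled windowed visit for analysis and reporting". No ET exception and no distance limit are visible. Total Mayo endpoints are treated differently: "we will use the same windows from the above table although total Mayo score was not assessed at each visit", with no forward move.

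**Dropouts.** For binary efficacy endpoints in subjects who discontinue, SAP 7.1 says "NRI will be used for missing data up to the visit" that "they would have reached if they had stayed at the study". Subjects who moved to Study A3921288 or to the Japan post-marketing study, or who left because of approval in Japan, get LOCF instead. For IBDQ remission, SAP 7.2 says "they will be handled in the same way as binary efficacy endpoints as specified in section 7.1 for missing data". SAP 8.2.5 summarizes PROs "using the same methods as for the efficacy endpoints for IBDQ".

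**Data collection.** Under Protocol 6.3, on withdrawal from treatment "the subject should complete the procedures listed at the Month 12/ET Visit". That list (Protocol 6.1.5) includes IBDQ. The Schedule of Activities places IBDQ at Months 2, 6, 12, 18, 24, 30 and 36, then only at Months 48, 60 and 72. Beyond that, "Annual schedule of activities are identical from year 4 and beyond". Partial Mayo score is scheduled at every visit after Month 36.

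**The concern.** An ET visit can fall on any day, so it often falls in a window with no scheduled IBDQ. Appendix 1 then relabels the score as belonging to the next scheduled visit. NRI acts only on missing data, and that visit is no longer missing. The dropout is reported by an on-treatment score instead of as a failure.

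An IBDQ total of at least 170 over time is a secondary endpoint in Protocol 2.2. At stake is whether its NRI proportion means the same as the NRI proportions for remission, mucosal healing and partial Mayo remission, where a dropout counts as a failure at later visits.

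**Working it through.** The plan gives no figure to reproduce. The check crosses the Appendix 1 windows with the protocol's IBDQ schedule.

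Formulas: days before the window opens = first day of receiving window − ET day; days before target = target day − ET day.

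| Receiving visit (target day) | ET days moved to it | Window opens | Days before opening | Days before target |
|---|---|---|---|---|
| Month 2 (60) | 2–45 | 46 | 1–44 | 15–58 |
| Month 6 (180) | 91–150 | 151 | 1–60 | 30–89 |
| Month 12 (360) | 226–315 | 316 | 1–90 | 45–134 |
| Month 48 (1440) | 1126–1395 | 1396 | 1–270 | 45–314 |
| Month 60 (1800) | 1486–1755 | 1756 | 1–270 | 45–314 |
| Month 72 (2160) | 1846–2115 | 2116 | 1–270 | 45–314 |
| Month ≥84 (2520) | 2206–2475 | 2476 | 1–270 | 45–314 |

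Months 18, 24, 30 and 36 give the same distances as Month 12. For Month 48: 1396 − 1126 = 270 and 1396 − 1395 = 1; 1440 − 1126 = 314 and 1440 − 1395 = 45. In Year 4 the moved days are 270 of the 360 days from Day 1126 to Day 1485, or 75%. Through Month 36 the share is 44% to 50%.

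**Worked case** (invented): a non-transfer dropout with ET on Day 1126 and an IBDQ total of 175, who would have reached Month 48.

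- IBDQ remission, windows applied and then imputation: the 175 fills Month 48, so remission.
- IBDQ remission without the move: Month 48 is missing, so NRI failure.
- Partial Mayo remission: the score is scheduled at Month 39 and stays there. Month 48 is missing, so NRI failure.
- Continuous IBDQ under LOCF: 175 at Month 48 either way.
- Observed-case IBDQ: 175 appears at Month 48 only because of the move.

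**Direction.** For a subject already in the NRI denominator, the move can turn a failure into a remission but never the reverse. A dropout who would not have reached the receiving visit before study end is different. Sections 7.1 and 7.2 leave that subject out of that visit, and the move adds the subject to the binary, continuous and observed-case summaries. A score below 170 then adds a non-remitter. Participation runs from about 4 to more than 7 years, so this applies mainly to Months 60, 72 and ≥84.

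**Size.** Among subjects in the NRI denominator, the change at Month 48 is (share with a non-transfer ET IBDQ on Days 1126–1395) × (share of those scoring ≥170). The documents give neither share. For scale only, if all 900 planned subjects were in the denominator (an assumption), each affected dropout would add 100/900 = 0.11 points, and 9 would add 9/900 = 1.0 point. In a smaller subpopulation fewer are needed. With wholly assumed inputs of 5 to 20 dropouts per 100 subjects over the 360 days, 75% of them in moved windows and 20% to 60% scoring ≥170, the range is 5 × 0.75 × 0.20 = 0.75 to 20 × 0.75 × 0.60 = 9.0 points. This shows how far the answer depends on unknown inputs. It is not an estimate.

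**The case against.** The strongest reply is that the rule is clear and deliberate. SAP section 6 assigns measurements to visits through the Appendix 1 windows, and imputation acts on what is then missing, so windowing naturally precedes imputation. Appendix 1 treats Mayo and PRO data in separate sentences, which suggests a choice. The study is descriptive, its primary objective is safety, and the listings keep all observations.

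Much of this stands. A reader might infer that the order of the two rules is simply unspecified, so that programmers would diverge. The documents do not support that firmly: the natural order is window and then impute, and parts of 7.1 and 7.2 are redacted. The change log and 7.2 both point to a dose-escalation rule in 7.1 that is not visible, so the hidden text may contain further handling rules. But the natural order produces the problem instead of removing it.

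A reader might also infer that IBDQ remission is always biased upward, or that LOCF summaries are never affected. Both fail for dropouts who would not have reached the receiving visit before study end.

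**Conclusion.** The concern holds as a flaw in a stated rule. Applied in the natural order, Appendix 1 places a departed subject's ET score at a visit whose window opens up to 270 days later (90 through Month 36), and so defeats NRI for IBDQ remission there. That is inconsistent with the handling of partial Mayo remission after Month 36 and of total Mayo endpoints.

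Its reach is narrow: one receiving visit per dropout, and for the NRI failure-to-remission change only ET scores of 170 or more. Subjects who moved to A3921288 or left under the Japan provisions already have LOCF, so the NRI conflict does not arise for them. Induction non-responders withdrawn at Month 2 have a modified ET visit without IBDQ. A large distortion might be inferred from the 75% of days affected, but the documents give neither dropout timing nor ET scores, so the size is unknown. No hypothesis test or safety conclusion is touched. The conclusion rests on the visible text. It is worth correcting because it concerns a protocol secondary endpoint and the correction is cheap.

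**What to change.** In SAP Appendix 1:

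- Exempt ET values of discontinued subjects from the forward move. Use an ET value at a scheduled visit only if it falls in that visit's own window. Otherwise report it as an ET or last on-study value.
- State that the NRI and LOCF rules of 7.1 and 7.2, including the limit to visits the subject would have reached, govern all visits after discontinuation.
- State that the ET value stays available as the LOCF source for continuous IBDQ and for subjects who moved to A3921288 or left under the Japan provisions. Without this, the exemption could be read as discarding it.

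The cost is a few sentences and a small change to visit-assignment programming, with no new data. IBDQ remission may be slightly lower at the receiving visits.

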Appendix 2. Further Definition of Endpoints

Appendix 2.1. Mayo Scoring System for Assessment of Ulcerative Colitis Activity

The Mayo Score ranges from 0 to 12, with higher scores indicating more severe disease. It consists of 4 subscores. Each sub-score ranges from 0 to 3. The 4 components of the Mayo Score are:

Stool Frequency:

- 0 = Normal no. of stools for this patient.
- 1 = 1 to 2 stools more than normal.
- 2 = 3 to 4 stools more than normal.
- 3 = 5 or more stools more than normal.

Rectal Bleeding:

- 0 = No blood seen.
- 1 = Streaks of blood with stool less than half the time.
- 2 = Obvious blood with stool most of the time.
- 3 = Blood alone passes.

Findings on Endoscopy:

- 0 = Normal or inactive disease.
- 1 = Mild disease (erythema, decreased vascular pattern).
- 2 = Moderate disease (marked erythema, lack of vascular pattern, any friability, erosions).
- 3 = Severe disease (spontaneous bleeding, ulceration).

Physician's Global Assessment:

- 0 = Normal.
- 1 = Mild disease.
- 2 = Moderate disease.
- 3 = Severe disease.

The subject's stool diary information will be captured by an interactive voice response system (IVRS) connected through the phone system. Subjects will report stool frequency and the most severe bleeding of the day for rectal bleeding subscore daily at least 5 consecutive days prior to each study visit during the study. Stool frequency subscore will be calculated based on the average number (rounded to an integer) of stools over the prior 3 days minus the normal number of stools per day reported by the subject. The rectal bleeding subscore is the average number (rounded to an integer) of the 3 days prior to the study visit.

CCI

CCI

CCI

Appendix 2.2.1. Inflammatory Bowel Disease Questionnaire (IBDQ)

The Inflammatory Bowel Disease Questionnaire (IBDQ) is a psychometrically validated patient reported outcome (PRO) instrument for measuring the disease-specific quality of life in subjects with IBD. The IBDQ consists of 32 items with scores ranging from 1 to 7 with 1 being the worst possible response and 7 being the best possible response.

The following endpoints will be derived based on the collected responses. In each instance, the change from Baseline values will be evaluated:

- IBDQ Total Score.
- IBDQ Domain Scores:
 - Bowel Symptoms;
 - Emotional Function;
 - Systemic Symptoms;
 - Social Function.

The Bowel Symptoms Domain score is calculated as the sum of the scores for questions 1, 5, 9, 13, 17, 20, 22, 24, 26 and 29 (Range 10-70).

The Emotional Function Domain score is calculated as the sum of the score for questions 3, 7, 11, 15, 19, 21, 23, 25, 27, 30, 31 and 32 (Range 12-84).

The Systemic Symptoms Domain score is calculated as the sum of the scores for questions 2, 6, 10, 14 and 18 (Range 5-35).

The Social Function Domain score is calculated as the sum of the scores for questions 4, 8, 12, 16 and 28 (Range 5-35).

The total IBDQ score is calculated as the sum of scores for questions 1 to 32 (Range 32-224) with a higher score indicating a better quality of life. Scores of patients with clinical remission usually range from 170 to 190.

C
C
I

C
C
I

[Redacted]

CCI

[Redacted]

CCI

CCI

CCI

CCI

CCI

CCI

CCI

CCI

CCI

CCI
